Study Drug administration ²¹				X	X	X	X		
Leakage Measure ²²				X	X	X	X		

1. Date of birth, gender, race, height (cm), weight (kg).
2. Medical History (including UC history) is to include the entire screening period, until just prior to the first dose of study drug with exception of AEs related to study procedures.
3. Blood pressure and heart rate at every visit (except visit 1b and 2a), body temperature, height and weight only at Visit 2b.
4. The following system organ classes will be reviewed for any relevant findings and appropriate physical examinations should be performed: general appearance, skin, musculoskeletal, eyes, ears, nose, throat, thyroid, cardiovascular, chest, abdomen, lymph nodes and neurological examination. Clinically significant findings will be reported as medical history prior to first dose of study drug and thereafter as an AE.
5. Haemoglobin, haematocrit, platelet count, RBC, WBC, platelets, neutrophil, eosinophil, basophil, lymphocyte, and monocytes count. Fibrinogen, APTT and PT (including INR) in non-fasting samples.
6. Albumin, alkaline phosphatase (ALP), alanine aminotransferase (ALT), aspartate aminotransferase (AST), amylase, blood urea nitrogen (BUN), calcium, chloride, creatine phosphokinase (CPK), creatinine, gamma glutamyl transferase (GGT), glucose, phosphorus, potassium, sodium, total bilirubin, total protein, uric acid, in non-fasting samples.
7. Total cholesterol and triglyceride, in non-fasting samples.
8. Blood, glucose, ketones, leucocytes, nitrite, protein, pH.
9. Stool culture of Clostridium difficile Toxin B, Shigella, Campylobacter, Yersinia and Salmonella, as well as ova and parasites.
10. Only for females of childbearing potential; Serum pregnancy test at screening visit 1a and then dip-stick tests at all other occasions.
11. Serum CRP and faecal calprotectin.
12. A 12 lead ECG will be done at screening visit 1a and visit 6. On visit 2b, ECG will be taken before study drug administration and 30 minutes after treatment.
13. A full colonoscopy will be required at visit 1b, and flexible sigmoidoscopy at primary endpoint, visit 6. Videos will be sent for central reading and biopsies collected for histopathological grading according the Nancy score and future biomedical research (if consented). 3 biopsies should be taken from each bowel segment investigated (see protocol section 7.7; separate instructions are provided).

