- Proportion of patients with clinical response at Week 6, defined as clinical remission or a three point and ≥ 30 % decrease from Baseline, Week 0 in the sum of the Modified Mayo score, i) rectal bleeding, ii) stool frequency and iii) endoscopy score (excluding friability), iiiii) physicians global assessment (PGA)
- Proportion of patients with a defecation urgency score of 0 or a decrease of at least one point in defecation urgency at Week 6 compared to Baseline, Week 0
- Mean change in faecal calprotectin at Week 1, 2, 3, and 6 compared to Baseline, Week 0
- Mean change in steroid dosage for patients in remission at Week 6 to Week 10
- Mean change in each of the inflammatory bowel disease questionnaire (IBDQ) sub domains at Week 6 compared to Baseline, Week 0

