6. STUDY SCHEDULE

6.1. Visit 1a (Day -14) and 1b (Day -7 to -10) – Screening Visits

The Screening period, will be divided in two separate visits, Visit 1a and 1b.

At the first Screening Visit, 1a the patient will in detail be informed about the study and if agreement to participate, an informed consent form (ICF) will be signed off before any study specific procedures occur (it is accepted that patient sign the ICF before first screening visit, maximum one week ahead and given repeated information at the first screening visit). During

the Screening Visit 1a, procedures to assure the patient's eligibility for the study participation will be performed. Demographics, (date of birth, gender and race), Vital Signs (blood pressure [BP], heart rate [HR], height, weight, smoking habits), medical history and UC history (including patient's normal number of stools/day when in remission) will be obtained. A physical examination will also be performed and a 12-lead ECG will be taken.

Non-fasting blood samples will be collected for haematology, blood chemistry including CRP (biomarker), lipid profile analysis and future biomedical research (if consented to). Urine sample will be collected for dipstick analysis (Blood, Glucose, Ketones, Leucocytes, Nitrite, Protein and pH) and if clinically significant microscopy and/or culture. Stool sample for culture, microbiology and biomarker's will also be collected. Females of childbearing potential will have a serum pregnancy test taken. Concomitant medications will be recorded. Prior UC treatment should be reported up to 3 years before screening visit and will be recorded with used dose; start/stop date and reason why not re-started to ensure inclusion criteria are fulfilled. The last treatment period of each UC drug will be collected. Allowed UC medications will be recorded with start date and dose to ensure stable dose is used during the entire study (GCS up to Week 6). Treatment with cyclosporine, methotrexate, TNF- α inhibitors, anti-integrins, tacrolimus or similar immunomodulatory/immunosuppressant drugs should have been stopped (at least 8 weeks before visit, 1a). These drugs should only have been stopped due to lack of efficacy or intolerable side effects. When laboratory results are available and the patient still is suitable for the study, patient will be informed about preparation for colonoscopy (separate instructions will be provided to the patient) which will be performed at screening visit 1b.

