The patient will before leaving the clinic also receive training and instructions how to use an electronic diary (eDiary) for daily entry of data up to the day before the randomisation Visit 2b.

At the second screening visit 1b a full colonoscopy will be performed in order to determine the extent of inflammation. The colonoscopy will be video recorded and send for central reading. During the endoscopy, three biopsy samples will be taken from each bowel segment investigated (ascending colon, transverse colon, descending colon, sigmoid colon, and rectum). These biopsies will be used for central read histopathological evaluation and for future biomedical research (if consented to, if not consented only two biopsies from each segment will be taken).

All inclusion and exclusion criteria will be reviewed at several time points before randomisation.

The interpretation from central reading of colonoscopy videos must be reviewed by the investigator to ensure eligibility prior to randomisation.

Any AEs related to study specific procedures will be recorded at the Randomisation Visit 2b.

PGA assessment should be done at visit 1b after the endoscopy. In case eDiary data are not available (3 days consecutive) the PGA can be done before visit 2a when randomisation occurs.

All obtained information will be reported in the eCRF.

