6.2. Visit 2a (Day -4 to-7) and 2b (Week 0) – Randomisation Visits

When the Central reading assessment is available and UC disease is qualifying for the study, the patient will be contacted by phone, Visit 2a, to ensure patient is willing to participate in

the study. If the patient is found to be eligible for study participation, the investigator will follow a central randomisation procedure and obtain a unique number (Patient Identification number) for the patient. If the patient fails to fulfil the inclusion/exclusion criteria, the patient can be re-screened at a later time point. If the re-screening will take place more than 1 month after the first screening visit all procedures need to be re-done, otherwise the Sponsor/CRO will confirm to site which screening procedures have to be repeated at re-screening in order to ensure that the patient fulfils the criteria for entering the study. If the re-screening is performed more than 1 month after the first screening, patient will receive a new Patient Identification number.

The patient must be scheduled for the Visit 2b/Week 0 visit within 10 days from the performed endoscopy (including the day of endoscopy and first treatment).

At the visit 2b; before study drug administration vital signs (HR, BP and temperature) and physical examination will be performed. Females of childbearing potential will take a dipstick urinary pregnancy test. An ECG will be taken before study drug administration and approximately 30 minutes after treatment, before leaving the clinic.

The patient will be asked to complete an IBDQ questionnaire and extra intestinal manifestations and defecation urgency assessment will be obtained. Non-fasting blood samples will be collected for haematology, blood chemistry including CRP (biomarker) and future biomedical research (if consented to). Urine sample will be collected for dipstick analysis (Blood, Glucose, Ketones, Leucocytes, Nitrite, Protein and pH) and if clinically significant microscopy and/or culture will be sent to central laboratory. Stool sample for faecal calprotectin (biomarker) will also be collected. Repeated training and instructions for the patient eDiary handling will be given. It is important to ensure the patient understands that eDiary data are necessary to evaluate the study. Information on concomitant medication will be collected. Any AEs related to study specific procedures, will be recorded.

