The patient will thereafter receive the study drug they were allocated to during the randomisation procedure. The study drug will be administered with a rectal enema. Following study drug administration the patient will be asked to remain recumbent for at least 30 minutes. Any leakage will be measured.

All obtained information will be reported in the eCRF.

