9.6. Exploratory Efficacy Endpoints Analyses

No multiplicity adjustments are made computing p-values of tests on exploratory variables; reported p-values are nominal. For overall comparison among more than two groups, the null hypothesis is that the proportions are the same in all groups.

The same analysis approach used for the primary efficacy endpoint will be applied to the exploratory efficacy variables referred to as a “Proportion endpoints”.

Continuous endpoints such as mean change from baseline will be evaluated using the ANCOVA, including treatment and stratifying factors as fixed factors and baseline as a covariate in the model.

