9.8. Adjustment of Covariates

Baseline values of the parameters to be analysed will be used as covariates in exploratory analyses. In addition, the prior use of TNF- α inhibitor and GCS use will be included as a covariate in exploratory analyses.

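### Faecal calprotectin is sampled twice before the first dose, but the planned ANCOVA adjusts only for the Week 0 value and leaves the Visit 1a value unused

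*Combined protocol and SAP*

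**What the plan says.** The endpoint in section 3.2.2 is "Mean change in faecal calprotectin at Week 1, 2, 3, and 6 compared to Baseline, Week 0". Section 9.6 evaluates continuous endpoints of this kind by ANCOVA, "including treatment and stratifying factors as fixed factors and baseline as a covariate in the model". Section 9.8 adds "Baseline values of the parameters to be analysed will be used as covariates in exploratory analyses", together with the two stratification factors. None of these passages mentions a screening value.

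Two calprotectin samples precede treatment:

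- **Visit 1a (Day -14).** Table 1 marks the biomarkers row at this visit, and its footnote 11 defines that row as "Serum CRP and faecal calprotectin". Section 6.1 agrees: "Stool sample for culture, microbiology and biomarker's will also be collected".
- **Visit 2b (Week 0).** Section 6.2 says "Stool sample for faecal calprotectin (biomarker) will also be collected". It then closes the visit with dosing: "The patient will thereafter receive the study drug they were allocated to during the randomisation procedure". The Week 0 value is therefore also pre-dose.

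Section 9.1 defers technical detail to a separate SAP, which is not part of the text reviewed here.

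**The concern.** A single stool value is an imperfect measure of a patient's pre-treatment level. A second value, taken before any dose, may explain outcome variation that the first misses. Because both precede treatment, adjusting for both does not bias the comparison of arms. The protocol pays for the Visit 1a sample and then gives it no role in the efficacy analysis. What is at stake is some precision in four comparisons of active drug with placebo, each with at most about 43 patients per arm.

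**Working it through.** **The plan's own figures.** The documents give no standard deviation, correlation or power for calprotectin. The only stated sample size is for the binary primary endpoint (section 9.2: 10% against 35%, one-sided 0.10, 90% power). With the pooled chi-square formula,

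n = [1.2816 × √(2 × 0.225 × 0.775) + 1.2816 × √(0.10 × 0.90 + 0.35 × 0.65)]² / 0.25² = [1.2816 × (0.5906 + 0.5635)]² / 0.0625 = 35,

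which matches the stated 35 per group. At 43 per group, two-sided 0.05 power is 80.4%, which matches the stated 80%. The 43 is used below only as an arm size. It is not a precision target for calprotectin.

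**Formula.** Let a be the correlation of the Week 0 value with the follow-up value, b that of the Visit 1a value with the follow-up value, and c the correlation between the two pre-dose values. With unit outcome variance:

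- one covariate: residual variance = 1 − a²
- two covariates: residual variance = 1 − (a² + b² − 2abc)/(1 − c²)
- relative reduction = (b − ac)² / [(1 − a²)(1 − c²)]

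The last line shows that the gain is exactly zero when b = ac, that is, when Visit 1a carries nothing beyond Week 0.

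**Results.** All correlations are assumptions.

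| a, b, c | One covariate | Two covariates | Variance cut | SE cut | 43 per arm acts like |
|---|---|---|---|---|---|
| 0.5, 0.35, 0.7 | 0.750 | 0.750 | 0% | 0% | 43 |
| 0.6, 0.5, 0.7 | 0.640 | 0.627 | 2.0% | 1.0% | 44 |
| 0.6, 0.5, 0.6 | 0.640 | 0.609 | 4.8% | 2.4% | 45 |
| 0.5, 0.5, 0.5 | 0.750 | 0.667 | 11.1% | 5.7% | 48 |
| 0.6, 0.6, 0.6 | 0.640 | 0.550 | 14.1% | 7.3% | 50 |
| 0.7, 0.7, 0.7 | 0.510 | 0.424 | 17.0% | 8.9% | 52 |

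The last column is 43 divided by the variance ratio. Worked example, second row: (0.5 − 0.42)² / (0.64 × 0.51) = 0.0064/0.3264 = 2.0%.

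**Simulation check.** I simulated five arms of 43 with two binary stratifiers. With 2,500 replicates the variance ratio was 0.92 when all correlations were 0.5 (formula 0.89) and 1.00 in the zero-gain case. With 20,000 replicates it was 0.893 and 1.006. The formula holds, and a useless second covariate costs about half a percent.

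**Two covariates or their mean.** For the mean as a single covariate, R² = [(a + b)/2]² / [(1 + c)/2]. At 0.5, 0.35, 0.7 this is 0.425²/0.85 = 0.2125. Residual variance is then 0.7875, against 0.750 with Week 0 alone, a ratio of 1.05. At 0.5, 0.3, 0.6 the ratio is 1.067. The mean can therefore be worse than Week 0 alone. Two separate covariates cannot be, apart from the one parameter.

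**Missing Visit 1a values.** If 5% of patients lacked that value (an assumption) and a complete-case model dropped them, variance would be multiplied by 1/0.95 = 1.053. The 2.0% cut then becomes a net ratio of 0.980/0.95 = 1.03, and the 4.8% cut becomes 0.952/0.95 = 1.00. The gain is cancelled unless missing covariates are handled.

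**The case against.** The strongest reply is that nothing is wrong. Change from the last pre-dose value, adjusted for that value, is a valid analysis that fits the endpoint as worded. The endpoint is one of many exploratory ones with nominal p-values, and no development decision rests on it. All of that stands. The point is an available improvement, not the repair of an error.

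The separate SAP might already use the Visit 1a value. That also stands: the statement that it goes unused is about the protocol text.

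The gain may be negligible. Equal correlation across all visits is generous when a Day -14 value is set against outcomes up to Week 6, and zero is possible. Section 6.2 also lets a patient re-screened within one month skip some procedures, so for some patients the Visit 1a value may be older than planned and less informative.

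A reader might infer more: that the Week 0 value is itself unsound, because it follows the Visit 1b colonoscopy, at which "three biopsy samples will be taken from each bowel segment investigated". The documents do not support that. Nothing in them says that bowel preparation or biopsy alters calprotectin at Week 0. The remark on preparation in section 9.5 concerns symptoms and the last two days before a visit. Even if there were such an effect, both samples precede dosing, so it would be expected equally in every randomised arm. It would add noise to the covariate and shift within-arm mean changes, without biasing the treatment contrast. It forms no part of the case.

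It is also tempting to let Visit 1a stand in as baseline when Week 0 is missing. That would contradict an endpoint defined as change from Week 0 and put the same value in both covariates.

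**Conclusion.** The point holds as a minor matter of precision. The protocol collects two pre-dose calprotectin values and adjusts for one. Adding the other would cut residual variance by about 0 to 17%, or 0 to 9% of the standard error. The upper end needs equal correlations of 0.7 at all visits. With correlations that decay over time, the cases worked give 2 to 5%, and the gain is nil if Visit 1a adds nothing beyond Week 0. A reader might take this for a bias, or for a threat to the trial's main conclusion. It is neither: the planned contrast is valid as it stands, and the primary endpoint and the trial size are unaffected.

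**What to change.** In section 9.6 or the SAP, before unblinding, state for faecal calprotectin that:

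1. Week 0 remains the baseline for the change endpoint.
2. The Visit 1a and Visit 2b values enter the ANCOVA as two separate covariates, not as their mean, on the scale used for the outcome.
3. A missing pre-dose value is filled by a prespecified imputation from the other pre-dose value, made without reference to treatment or outcome, so that no patient is dropped. A rule is also needed for a patient with neither value. Section 9.9 does not cover this case: non-responder imputation defines no value for a continuous biomarker, and section 9.10 permits exclusion where no imputation algorithm is described.
4. Where Week 0 is missing, the follow-up value is modelled with both covariates, rather than computing change from a different baseline. With Week 0 in the model, change and follow-up give the same treatment contrast, because subtracting a covariate from the outcome alters only that covariate's coefficient. The rule is therefore compatible with item 1.

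The cost is a few sentences and one degree of freedom. No visit, sample or assay is added. Fixing it before unblinding matters because a covariate added later would look data-driven.

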9.7. Safety Analysis

9.7.1. Analysis of Adverse Events

The number and percentage of patients reporting AEs, and the number of AEs reported will be presented. The events will be tabulated by system organ class and preferred term. In addition, summaries by relationship to study drug and severity will be presented. SAEs will also be presented in separate tabulations.

The number of patients experiencing an AE will be compared descriptively between groups.

All patients with AEs will be listed individually with patient number in addition to type of event, start and stop time, duration, seriousness, severity, action taken, relationship to study drug and outcome of AE.

9.7.2. Other Safety Assessments

All continuous safety variables, such as laboratory measurements, vital signs, ECG parameters, and body weight will be described using summary statistics. Changes from baseline will also be summarised as appropriate.

All categorical variables, such as physical examination, will be summarised using frequencies and percentages.

The safety will include laboratory safety variables and/or adverse clinical findings as appropriate. Laboratory data will also be presented in shift tables for selected parameters,

where the number of values within, below and above laboratory reference range will be displayed.

9.8. Adjustment of Covariates

Baseline values of the parameters to be analysed will be used as covariates in exploratory analyses. In addition, the prior use of TNF- α inhibitor and GCS use will be included as a covariate in exploratory analyses.

9.9. Handling of Dropouts and Missing Data

For the efficacy analyses, missing data will be replaced using the non-responder imputation (NRI). NRI will be used where missing data are replaced with a negative outcome, i.e. interpreted as a non-responder to the intervention, e.g. no clinical remission in the primary endpoint. The last-observation-carried-forward will be used as a sensitivity analysis for evaluation of study data. Additional methods for handling missing data will be used and described in the Statistical Analysis Plan (SAP).

9.10. Rules for Excluding Patients from Analysis

Patients will not be excluded from any analyses unless they fall outside a specific definition of the populations described earlier, or unless there is missing data for all endpoints for which an imputation algorithm is not described. Protocol deviations will be described in a separate document for the purposes of defining the Per Protocol Set prior to database lock.

9.11. Procedures for Reporting Deviations from Original Statistical Plan

Any deviations from the original SAP will be described and justified in the final study report.

9.12. Interim Analysis

No formal statistically based interim analysis will be performed. However, the safety data will be reviewed periodically during the conduct of the study by the independent DSMB. The primary objective of the DSMB data review is safety.

10. DATA HANDLING

10.1. Data Handling

██████████ will be responsible for the processing and quality control of the data. Data management will be carried out as described in ██████████ SOPs for clinical studies. Handling of data, including data quality control, will comply with regulatory guidelines (e.g., ICH and GCP) and ██████████ SOP and working instructions. The Data Management procedures will be detailed in a written Data Management Plan approved by InDex Pharmaceuticals AB.

All source data will be identified at the start of the trial. eDiary data and laboratory data will be considered as source data, all other data will be entered in eCRF by Site staff based on the Source data. Data Management routines include procedures for handling the eCRF, database set up and handling, data verification and entry, data validation, database quality control and documentation of activities performed, including information on discrepancies in the procedure.

The investigator must ensure the accuracy, completeness, legibility, and timeliness of data reported in the eCRF and all required reports. Any change or correction to the eCRF must be dated, signed and explained (if necessary) and must not obscure the original entry. This process applies to both written and electronic changes.

eCRF reported data that are derived from source documents should be consistent with the source documents, or the discrepancies must be explained.

Within three days of completion of each patient visit, the investigator should agree to have completed and entered data into eCRF for inspection by the clinical monitor.

All of the AEs (whether serious or not) described in the eCRF will be entered in the study database.

The initial notification of SAEs will also be entered in the [REDACTED] safety database for coding, medical evaluation and notification to the health authorities and independent ethics committees (EC) according to national regulatory requirements.

